8.3.2 Serious Adverse Events

A serious adverse event (SAE) is any adverse event/experience occurring between baseline assessments and the patients final study visit that results in any of the following outcomes and is considered by the investigator(s) to be unexpected or not consistent with the natural history of the disease:

- Death
- Life threatening (subject at immediate risk of death)
- Requires inpatient hospitalization or prolongation of existing hospitalization
- Results in a persistent or significant disability or incapacity
- Important medical events that may not result in death, be life threatening, or require hospitalization may be considered SAEs when, based upon appropriate medical judgment, may jeopardize the subject and may require medical or surgical intervention to prevent one of the outcomes listed in this definition.

All the unexpected SAE will be promptly (within 24 hours) reported to the local IRB and DSMB (see reporting procedures). The DSMB report to the investigators will be forwarded to the NHLBI Program Officer, including the discussion of the concerns, and the basis for any recommendations that the DSMB has made in response to the concerns (within 7 calendar days if fatal or life-threatening unexpected, suspected serious adverse reactions; or within 14 days for unanticipated problem that is not an SAE or within 15

calendar days for all non-fatal, non-life threatening unexpected, suspected serious adverse reactions, or within 30 days of receipt of the DSMB or IRB report for all other unanticipated problems or scheduled meetings).

8.4 Reporting Procedures

8.4.1 Serious Adverse Events

All unexpected AEs that result in death or are otherwise reportable SAEs or AEs will be reported promptly to the Data Safety Monitoring Board (DSMB) and the IRB within 1 business day of investigators becoming aware of the event. AEs (serious or non-serious) that transpire secondary to an overdose must also be reported to the DSMB within 1 business day of knowledge of the event, using an AE form. The SAE form will always be completed as thoroughly as possible with all available details of the event, signed by the investigator (or designee), and, if a reportable adverse event as defined herein, forwarded to the DSMB within the designated time frames. If the investigator does not have all information regarding an SAE, he/she will not wait to receive additional information before notifying the DSMB of the event and completing the SAE form. The form will be updated when additional information is received. The investigator will always provide an assessment of causality at the time of the initial report.

8.5 AE/SAE Data Collection

When an AE/SAE is suspected, it is the responsibility of the investigator(s) to review all documentation (e.g., hospital progress notes, laboratory and diagnostic reports) relative to the event. The investigator will then record all relevant information regarding a suspected AE/SAE on the AE form. The investigator will attempt to establish a diagnosis of the event based on signs, symptoms, and/or other clinical information. In such cases, the diagnosis should be documented as the AE/SAE and not the individual signs/symptoms.

8.6 The Data and Safety Monitoring Board (DSMB)

For this study, the DSMB is composed of a coordinator, 5 voting members (see DSMB Chapter in the Appendix), chaired by a cardiologist from University of Florida in Jacksonville, Florida, who has extensive clinical trial experience, and including an infectious disease specialist, an immunologist, a heart failure specialist, and a biostatistician. The composition of the DSMB will have been reviewed and approved by the VCU IRB. The DSMB will meet every 6 months or sooner in case of unanticipated serious adverse events. The DSMB coordinator will provide the board members with data regarding screening, enrollment, adverse events and withdrawals, and he/she will not participate in the voting. The board members may request unblinding at any time. Upon request of the DSMB (following positive vote by 3 or more members), the coordinator will retrieve the randomization code for one or more individual patients (as needed). If necessary the DSMB will inform the investigators of the unblinding of the randomization code, if not necessary the investigators (and the patients) will be kept blinded. The DSMB

may request an expert opinion by one or more non-members, however only the DSMB members will vote on any individual issue. The DSMB (following positive vote by 3 or more members) may request temporary or permanent halting of the study (see halting rules), or interruption of treatment of one or more patients. The minutes from each meeting will be distributed to the board members, NHLBI Program Officer, and to the IRB, and not to the investigators unless specifically requested by the DSMB. A brief conclusive statement addressing whether the study should continue as planned or not will be provided to the investigators and the IRB every 6 months. The investigators will provide the NHLBI staff with reports from the DSMB and the IRB in a timely fashion (within 7 calendar days if fatal or life-threatening unexpected, suspected serious adverse reactions; or within 15 calendar days for all non-fatal, non-life threatening unexpected, suspected serious adverse reactions, or within 30 days of receipt of the DSMB or IRB report for all other unanticipated problems or scheduled meetings). See Appendix – DSMB Chapter.

8.7 Regulatory Reporting

This study is conducted in accordance to the NIH Good Clinical Practice guidelines. An Investigational New Drug use waiver from the Division of Cardiovascular & Renal Products, Center for Drug Evaluation & Research, Food & Drug Administration was given to [name]. The study protocol, consent, and Data and Safety Monitoring Plan will have been approved by the VCU IRB prior to study initiation. The investigators will provide the NHLBI staff with reports from the DSMB and the IRB in a timely fashion (within 7 calendar days if fatal or life-threatening unexpected, suspected serious adverse reactions; or within 15 calendar days for all non-fatal, non-life threatening unexpected, suspected serious adverse reactions, or within 30 days of receipt of the DSMB or IRB report for all other unanticipated problems).

8.8 Type and Duration of Follow-up of Subjects after Adverse Events

All AEs and SAEs will be followed until resolution, until the condition stabilizes, until the event is otherwise explained, whichever occurs first. All AEs and SAEs documented at a previous visit/contact and designated as ongoing, will be reviewed at subsequent visits/contacts, where the designation may remain ongoing. The investigator will ensure that the follow-up includes any supplemental investigations as may be indicated to elucidate the nature and/or causality of the SAE. This may include additional laboratory tests or investigations, histopathological examinations, or consultation with other health care professionals. SAEs that are ongoing at the time of the subjects' final study visit/contact will be documented as ongoing.

8.9 Halting Rules

The DSMB will monitor the progress of the present trial. No interim efficacy analyses are planned; however, an interim analysis could be performed at any time to assess efficacy and futility, if requested by the 3 or more members of the DSMB. The DSMB will meet regularly to review safety data every 6 months (or sooner in case of unanticipated serious

adverse events). All meetings and actions taken by the committee will be recorded along with the reasons for the actions. These documents will include any data summaries or analyses provided to the DSMB and will remain confidential until the study is concluded. The DSMB may choose to stop enrollment on the basis of safety data observed. If safety concerns are found, further enrollment will not be allowed until issues are resolved. If no safety concerns are found, enrollment will continue until the target sample size is reached.

9) ADJUDICATION OF CLINICAL EVENTS

9.1 Event-adjudication committee

The event-adjudicating committee will be composed of professionals from different backgrounds including general cardiologists, cardiologists with training in heart failure, general internal medicine specialists, emergency medicine specialists, and infectious disease specialists. Each event will be reviewed by at least 3 members. Agreement will be necessary for all 3 members, disagreement will be resolved with discussion of the case, followed by voting of at least 5 members if disagreement remains. The committee will meet at the end of the study and review all adjudicated events. The committee will be blinded to treatment allocation. In order to favor allocation concealment, the committee will also be blinded to C-reactive protein levels, which may be affected by treatment.

9.2 Definition of the events

The events adjudicated will include:

- Death;
- Cardiac death (in which a direct cause attributable to cardiac disease is present);
- Sudden cardiac death (in which cardiac death occurred out of the hospital and suddenly; or in the hospital due to ventricular arrhythmias unrelated to other concomitant cardiac conditions);
- Non-cardiac death (in which the event of death is considered not to be a direct consequence of cardiac disease);
- Hospitalization for any cause;
- Hospitalization for heart failure (in which the primary diagnosis for hospitalization is decompensated heart failure established as the finding at admission of all 2 conditions listed: *a.* dyspnea or respiratory distress or tachypnea at rest or with minimal exertion; *b.* evidence of elevated cardiac filling pressure or pulmonary congestion (at least one of the conditions must be met: pulmonary congestion/edema at physical exam OR chest X-ray; plasma BNP levels ≥ 200 pg/ml; or invasive measurement of left ventricular end-diastolic pressure > 18 mmHg or of pulmonary artery occluding pressure (wedge) > 16 mmHg);
- Outpatient worsening of heart failure (defined as the need for intravenous diuretic treatment or need for increase in oral diuretic dose, or new prescription for first or add-on diuretic);
- Acute myocardial infarction, as defined by the WHO consensus statement 4th edition;
- Unstable angina, or need for coronary revascularization;

- Cardiac tachy-or brady-arrhythmias leading to a new hospitalization or to prolongation of hospital stay;
- Acute renal failure (defined as an increase in plasma creatinine levels of 50% or 0.5 mg/L);
- Acute respiratory failure (not due to heart failure);
- Sepsis or other serious infection requiring antibiotic therapy;
- Acute stroke.

The analysis will consider time to first event and time to each event. It will also consider event rates at 1, 3 and 6 months, in order to favor comparisons with other studies. The number of days free of hospitalization during the first 1, 3 and 6 months will also be measured and compared between groups.

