Interleukin-1 Blockade in Recently Decompensated Heart Failure

A Randomized Placebo-controlled Double-blinded Study

The REDHART2 study

STUDY PROTOCOL

Principal Investigators:
[name], PhD;
[name] [name]

Virginia Commonwealth University

CHANGES TO PRIOR VERSION

Prior version dated 10-25-2018 → new version 11-13-2018

- Personnel updated in the DSMB Charter per NHLBI Liaison request (see also section 8.6, and DSMB charter);
- Modified BNP criteria to include also NT-proBNP criteria – according to the European Society of Cardiology 2016 Heart Failure Guidelines (Ponikowski P et al. Eur Heart J 2016;37:2129-2200.

Prior version dated 11-13-2018 → new version 01-23-2019

- **Section 5.2:** Addition of the IPAQ questionnaire to the quality of life assessments. It will be administered at baseline, 6, 12 and 24 weeks to assess patient perception of changes
- **Section 6.3:** Changed exclusion criteria from “prior or current malignancy” to just “current malignancy receiving targeted therapy”.
- **Section 7.1:** We clarify that the patient may need to come for additional visits between the pre-specified clinic visits for assessment and/or drug dispensing.
- **Section 7.7:** Addition of the IPAQ questionnaire to the list of study activities and clarification on when a physician will be alerted to review a participant’s chart based on questionnaire responses.
- **Section 11.3.2:** Clarification on when cases with missing CPX data will result in omission from efficacy analysis.

DSMB Charter 3.f.: Clarification of the Biostatistician as Voting Member of the DSMB.

Prior version dated 01-23-2018 → new version 03-14-2019

- **Section 5.2:** Updated echocardiography description to include 6 and 12 week ECHO timepoints
- **Sections 7.5 and 7.9:** Updated echocardiography paragraph and procedure table to include ECHOs at weeks 6 and 12
- **Section 7.8:** Removed “troponin I” from text as biomarker being tested

Prior version dated 03-14-2019 → 08-27-2019

- Section 6.3: Clarified exclusion criterion related to CRT and valve surgery ('Cardiac resynchronization therapy (CRT) during index hospitalization, or planned CRT or valve surgeries within the following 6 months').
- Section 7.9: Corrected the time window for Visit 4 to 168 ± 14 days (24 ± 2 weeks).
- Section 8.3.1: We have updated the AE section to list the most common risks related to anakinra or completion of the study procedures.

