5.2 Secondary Exploratory Endpoints

Secondary exploratory endpoints will include parameters measured at CPX, echocardiography, non-invasive hemodynamics, as well as biomarkers, and clinical outcomes.

Additional CPX parameters: secondary endpoints include changes in peak VO₂ at earlier endpoints (6 and 12 weeks), and changes in other CPX variables such as ventilatory efficiency (ventilation-carbon dioxide elimination slope [VE/VCO₂ slope]) and oxygen utilization efficiency slope [OUES]), anaerobic threshold, and peak oxygen pulse at 6, 12, and 24 weeks.

Echocardiography: secondary endpoints include measuring left ventricular end-diastolic and end-systolic volumes, ejection fraction, stroke volume estimated by left ventricular outflow tract velocity-time integral, measures of myocardial relaxation at tissue Doppler E', and estimate of left ventricular filling pressure using E/E' ratio at baseline, 6, 12 and at 24 weeks.

Non-invasive hemodynamics: secondary endpoints include estimates of arterial elastance (E_a), a measure of afterload, end-systolic elastance (E_{es}), a measure of load-independent contractility also defined as end-systolic pressure-volume relationship,

ventriculo-arterial coupling is defined as the ratio of E_a to E_{es} , at 6, 12 and 24 weeks. The hemodynamic assessment will be conducted with echocardiography and non-invasive blood pressure measuring.

Quality of life assessment: the Duke Activity Status Index (DASI), the Kansas City Cardiomyopathy Questionnaire (KCCQ), the International Physical Activity questionnaire (IPAQ-SF) and the Patient Health Questionnaire-9 (PHQ-9) will be administered at baseline, 6, 12 and 24 weeks to assess patient perception of changes.

Biomarkers: Blood will be collected at each visit (baseline, 6, 12, and 24 weeks) and analyzed for a panel of complete blood cell count with differential, basic metabolic panel, high sensitivity C- reactive protein (CRP), and NT-proBNP. In addition, 5 – 10mL of blood will be stored frozen for later batch analysis and phenotyping of the inflammatory response .

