6.1 Screening

Patients will be screened through one of the following routes:

- Patients admitted to the main VCUHealth hospital in Richmond, VA

Our hospital receives >1000 hospitalizations per year for acute decompensated systolic heart failure, of which, we anticipate approximately 30 per month (~36%) will be preliminary eligible for REDHART2 participation. These subjects may be identified by multiple means: direct patient contact by the co-PIs or one of the co-investigators during their regular clinical practice, referral to the research team by coworkers or by the HF Navigator Nurse (a program set to establish post-discharge follow up care for patients), manual screening of the new daily admission list on the electronic medical record by research team, and an automatic alert system generated by the electronic medical record that identifies all new cases that meet pre-specified criteria (i.e., receiving intravenous diuretics, BNP>200 ng/mL, edema on chest radiography). We have been using these strategies for clinical enrollment over the past 3 years. While the system may not be specific (many false positive alerts – screen failures) it is very sensitive with virtually no HF-patient being lost to evaluation.

- Patients admitted to neighboring hospitals in Virginia

Being the only academic medical center in Central Virginia we receive a large number of referrals for inpatient transfers or for outpatient evaluations, i.e., after acute decompensation, especially in underserved population such as the uninsured. In the

recent years, VCUHealth has partnered with the Community Memorial Hospital in South Hill, VA (a 200-bed hospital in the southern corridor of I-85) and with the Virginia Medical Group in Colonial Heights, VA (including a specialized cardiac center with 7 specialists).

- Post-hospital discharge clinics

We have implemented a dedicated clinic for heart failure patients to be seen in clinic within 1 week of hospital discharge as part of the HF Navigator program. This clinic is staffed by a nurse practitioner and a nurse, and supervised by a HF specialist. The research team has access to the daily scheduling list and thus has access to those patients that may have been missed during hospitalization or that may be following up after hospitalization at a different hospital.

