6.2 Inclusion Criteria

All 6 criteria need to be met for enrollment of the patient in the study

1. Primary diagnosis for hospitalization is decompensated heart failure established as the finding at admission of both conditions listed below:
 - dyspnea or respiratory distress or tachypnea at rest or with minimal exertion;
 - evidence of elevated cardiac filling pressure or pulmonary congestion (at least one of the conditions must be met):
 - pulmonary congestion/edema at physical exam OR chest X-Ray;
 - plasma BNP levels ≥ 200 pg/mL or proBNP ≥ 600 pg/ml;
 - invasive measurement of left ventricular end-diastolic pressure > 18 mmHg or of pulmonary artery occluding pressure (wedge) > 16 mmHg.
2. The patient has a prior documentation of impaired left ventricular systolic function (ejection fraction $\leq 40\%$) at most recent assessment by any imaging modality (within 12 months).
3. The patient is now clinically stable, euvolemic, and meets standard criteria for hospital discharge as documented by all the 3 conditions listed below:
 - absence of dyspnea or pulmonary congestion/distress at rest;
 - absence of pitting edema in the lower extremities, or in any other region;
 - stable hemodynamic parameters (blood pressure, heart rate).
4. The patient is of age ≥ 21 years old, and is willing and able to provide written informed consent.
5. The patient is willing and able to comply with the protocol (i.e., self-administration, or exercise test).
6. The patient has screening high sensitivity plasma C-reactive protein levels (hsCRP) > 2 mg/L.

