7.8 Biomarkers assessment

Blood samples will be taken from a peripheral vein at time of screening, baseline visit, 2, 6, 12 and 24 weeks, and used for analysis of complete cell count with differential, comprehensive metabolic profile [including inflammatory markers] and cardiac specific biomarkers [NT-proBNP]. Testing will be performed at VCUHealth, with the exception of research-only inflammatory markers, for which the samples will be processed and stored

for single batch analysis at the end of the study. Research-only biomarkers will not be used for clinical care and will not be shared with the patient nor with the referring providers.

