7.9 Study Schedule

	Screening (≤14 days from discharge)	Visit 1 (Baseline)	Visit 1.5 (14±3 days)	Visit 2 (42±7 days)	Visit 3 (84±7 days)	Visit 4 (128±14 days)
Visit location	Hospital or CRSU	CRSU	CRSU***	CRSU	CRSU	CRSU
Screening *	X					
Consent	X					
Clinical assessment **	X	X	X	X	X	X
Medication reconciliation	X	X		X	X	X
Investigational therapy dispensing		X		X	X	
CPX		X		X	X	X
Echocardiogram		X		X	X	X
Non-invasive hemodynamics/ Bio-Impedance		X		X	X	X
Safety labs (CBC, renal function)		X	X	X	X	X
Biomarkers (hsCRP, NTproBNP)		X		X	X	X

*Includes hsCRP - Pregnancy test will be performed, if indicated

**Clinical assessment includes history and physical, medication reconciliation, and assessment of adverse events

***Visit 1.5 may happen in the CRSU or in other clinics with the patient's own provider.

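### The natriuretic peptide limb of the heart failure hospitalization outcome (9.2) omits the proBNP alternative that the matching limb of inclusion criterion 1 (6.2) allows

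*Combined protocol and SAP*

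**What the plan says.** Inclusion criterion 1 (6.2) and the heart failure hospitalization outcome (9.2) share one structure. Each requires decompensated heart failure as the primary diagnosis, established at admission by (a) a respiratory symptom or sign and (b) evidence of congestion or raised filling pressure. Any one of three limbs satisfies (b): congestion on examination or chest X-ray, a natriuretic peptide threshold, or an invasive pressure (above 18 mmHg end-diastolic or above 16 mmHg wedge).

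- Peptide limb at entry (6.2): "plasma BNP levels ≥ 200 pg/mL or proBNP ≥ 600 pg/ml".
- Peptide limb for the outcome (9.2): "plasma BNP levels ≥ 200 pg/ml".
- The other routes in 9.2 remain open: "at least one of the conditions must be met: pulmonary congestion/edema at physical exam OR chest X-ray", and the invasive pressures.

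The list of changes at the front of the protocol records, for the version of 11-13-2018, "Modified BNP criteria to include also NT-proBNP criteria". That entry gives no section number. Section 5.2 says that the committee is blinded to allocation and works from the whole chart. Section 9.3 places adjudication after the study is complete.

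**The concern.** Two definitions that appear intended to match do not. A patient can enter the trial on an admission documented by proBNP, be readmitted with the same findings, and not be counted as a heart failure hospitalization.

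The protocol wants this outcome for a purpose. Section 4 says the trial will explore the possible effect size on heart failure readmission. Section 11.1 says a readmission signal would strengthen the case for phase III. Section 9.2 wants event rates that can be compared with other studies. A rate that depends in part on which peptide was ordered serves these uses less well.

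There is also a practical difficulty. Section 9.1 asks three members to agree on each event. Faced with a proBNP value and no threshold for it, members must either apply the text literally or choose their own cut-off.

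**Working it through.** **Text comparison.** Both definitions are current text.

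| Element | Entry, 6.2 criterion 1 | Outcome, 9.2 |
|---|---|---|
| (a) respiratory symptom or sign | required | required, same content |
| (b) congestion on examination or chest X-ray | qualifies | qualifies |
| (b) BNP ≥ 200 | qualifies | qualifies |
| (b) proBNP ≥ 600 | qualifies | not listed |
| (b) invasive pressure, >18 or >16 mmHg | qualifies | qualifies |

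Only the proBNP row differs. An admission is classified differently only if all of these hold: (a) is met; examination and X-ray show no congestion; no invasive pressure qualifies; proBNP is at least 600 pg/ml; and BNP was not measured.

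**Size.** The plan states no event count, rate assumption or power for heart failure hospitalization, so there is no figure to reproduce. What follows is an illustration.

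Inputs: 34 placebo and 68 anakinra patients (11.2); pilot six-month readmission of 30% on placebo and 5% on 12 weeks of anakinra (section 4). The pilot figure is described as hospital readmission, so using it as a heart failure rate is an assumption. Let f be the share of true events whose only evidence for (b) is proBNP. The documents do not give f. It is varied here and taken as equal in both arms.

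Expected events at f = 0: 34 × 0.30 = 10.2 and 68 × 0.05 = 3.4. Counted events are these multiplied by (1 − f). The counted rates are p1 = 0.30(1 − f) and p2 = 0.05(1 − f), so the risk difference is 25(1 − f) percentage points. The rate ratio, 0.05/0.30, does not change with f.

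Nominal power for two proportions, two-sided 0.05, is Φ{[(p1 − p2) − 1.96·SE0]/SE1}. Here SE0 = √[p̄(1 − p̄)(1/34 + 1/68)], SE1 = √[p1(1 − p1)/34 + p2(1 − p2)/68], and p̄ is the pooled rate over 102 patients.

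- f = 0: p̄ = 13.6/102 = 0.133, SE0 = 0.0714, SE1 = 0.0829; (0.25 − 0.1399)/0.0829 = 1.33, power 0.91.
- f = 0.10: p̄ = 12.24/102 = 0.120, SE0 = 0.0683, SE1 = 0.0802; (0.225 − 0.1338)/0.0802 = 1.14, power 0.87.

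| f (assumed) | Placebo events counted | Anakinra events counted | Risk difference, points | Nominal power |
|---|---|---|---|---|
| 0 | 10.2 | 3.4 | 25.0 | 0.91 |
| 5% | 9.7 | 3.2 | 23.75 | 0.89 |
| 10% | 9.2 | 3.1 | 22.5 | 0.87 |
| 20% | 8.2 | 2.7 | 20.0 | 0.83 |
| 30% | 7.1 | 2.4 | 17.5 | 0.77 |

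The power column shows direction only. The approximation is rough with about 3 expected events in one arm, the planned test is a log-rank test, and 11.1 says the trial is not powered for admission rates.

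**The case against.** The case for leaving this alone is that it will rarely matter. Most of that case stands.

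- A reader might infer that the whole outcome accepts only BNP. It does not: congestion on examination or chest X-ray qualifies, as does an invasive pressure. Only the peptide limb is narrower.
- A reader might infer that proBNP will be the usual value at readmission because the trial measures NT-proBNP ("high sensitivity C- reactive protein (CRP), and NT-proBNP" in 5.2; likewise 7.8 and 7.9). Those samples are taken at screening and scheduled study visits, whereas 9.2 concerns findings at admission. The one hospital-side peptide named is BNP, in the main hospital's alert in 6.1: "receiving intravenous diuretics, BNP>200 ng/mL, edema on chest radiography".
- A reader might infer that assays differ between hospitals, since 6.1 lists neighboring hospitals and patients first admitted elsewhere. The documents say nothing about those hospitals' assays or about where readmissions occur. Variation is possible but not documented.
- A reader might infer bias toward one arm. The rule is the same in both arms and adjudication is blinded, so nothing points to a direction.
- An affected admission is not lost. It still counts as a hospitalization for any cause and in days free of hospitalization.

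Two replies do not succeed. Access to the whole chart (5.2) settles what evidence is seen, not which threshold applies, so it does not supply the missing proBNP limb. Nor is this merely a change-log discrepancy: the log suggests a cause, but the conflict is between 6.2 and 9.2 as they now stand.

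**Conclusion.** The inconsistency is real and follows from the text alone. The proBNP alternative is in the entry criterion and missing from the outcome definition. The likeliest explanation is that the 11-13-2018 change was not carried into 9.2.

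Its effect is limited to readmissions where proBNP, without BNP, is the sole evidence for condition (b). Their number is unknown and may be close to zero. Under the pilot rates, each 10% of events so affected costs about 1.0 placebo and 0.3 anakinra events. If the share is equal in the two arms, the rate ratio is unchanged while the absolute rates and their difference shrink in proportion. The primary endpoint, the sample size and the power table in 11.2 are untouched.

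This is a modest correction to an exploratory outcome. It is worth making because expected events are few and the change is nearly free.

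**What to change.** Before adjudication and unblinding, reconcile condition (b) of heart failure hospitalization in 9.2 with inclusion criterion 1 in 6.2 by using the same peptide limb in both. If the difference is intended, state the reason.

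Name the assay consistently at the same time. Section 6.2 says proBNP, while the change log and sections 5.2, 7.8 and 7.9 say NT-proBNP. Copying the 6.2 wording unchanged would carry that ambiguity into the outcome.

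Apply the agreed text to every event. The cost is a few words in 9.2 and on the adjudication form, plus the assay name in 6.2 if that is changed. No new data are needed, and because adjudication comes after study completion, all events can be judged under one definition.

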Clinical outcomes: the incidence of death (cardiac and non-cardiac), hospitalizations (for HF, for other cardiac causes not related to HF, for non-cardiac reasons), medications use (number of HF medications, doses) will be recorded at each visit in every patient. Adjudication of events for research purposes will be performed by an *ad hoc* committee blinded to treatment allocation, based on all the data available in the chart including notes, pre-formatted sheets, laboratory and imaging modalities.

6) ENROLLMENT IN THE STUDY

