6.3 Exclusion Criteria

Subjects will not be eligible if they meet any one of the following 15 exclusion criteria.

1. The primary diagnosis for admission is NOT decompensated heart failure, including

- diagnosis of acute coronary syndromes, hypertensive urgency/emergency, tachy- or brady-arrhythmias.
- 2. Concomitant clinically significant comorbidities that would interfere with the execution or interpretation of the study including but not limited to acute coronary syndromes, uncontrolled hypertension or orthostatic hypotension, tachy- or brady-arrhythmias, acute or chronic pulmonary disease or neuromuscular disorders affecting respiration.
- 3. Cardiac resynchronization therapy (CRT) during index hospitalization, or planned CRT or valve surgeries within the following 6 months.
- 4. Previous or planned implantation of left ventricular assist devices or heart transplant.
- 5. Chronic use of intravenous inotropes.
- 6. Recent (<14 days) use of immunosuppressive or anti-inflammatory drugs (including oral corticosteroids at a dose of prednisone equivalent of 0.5 mg/kg/day but not including inhaled or low dose oral corticosteroids or non-steroidal anti-inflammatory drugs).
- 7. Chronic inflammatory disorder (including but not limited to rheumatoid arthritis, systemic lupus erythematosus).
- 8. Active infection (of any type), including chronic/recurrent infectious disease (i.e. HBV, HCV, and HIV/AIDS) – but excluding HCV+ with undetectable plasma RNA.
- 9. Evidence of COVID19 within the last 60 days or recent (21 days) exposure to close personal contact.
- 10. Current malignancy (excluding carcinoma in situ [any location] or localized non-melanoma skin cancer) receiving targeted therapy
- 11. Any comorbidity limiting survival or ability to complete the study.
- 12. Stage V kidney disease or on renal-replacement therapy.
- 13. Neutropenia (<1,500/mm³ or <1,000/mm³ in African-American patients).
- 14. Pregnancy.
- 15. Angina, hypertension, arrhythmias, electrocardiograph (ECG) changes, or other non-cardiac limitations (i.e., peak respiratory exchange ratio VCO₂/VO₂ [RER]<1.0, reflecting sub-maximal test) that limit maximum exertion during CPX obtained during the baseline testing.
- 16. Hypersensitivity to Kineret or to E. coli derived products.

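### The absolute limb of the acute renal failure definition (0.5 mg/L creatinine, which is 0.05 mg/dL) makes the 50% limb redundant and points to a unit error

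*Combined protocol and SAP*

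**What the plan says.** Section 9.2 gives two alternative criteria for this event, one relative and one absolute: "Acute renal failure (defined as an increase in plasma creatinine levels of 50% or 0.5 mg/L"). It names no reference creatinine, time window or confirmatory sample, and no other section restates or corrects the unit.

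On use of the event, section 9.2 states: "The analysis will consider time to first event and time to each event". It adds event rates at 1, 3 and 6 months, meant to ease comparison with other studies.

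On measurement, the schedule in section 7.9 has a row "Safety labs (CBC, renal function") marked at baseline and at Visits 1.5, 2, 3 and 4. That gives one baseline value and four later ones. On renal eligibility, section 6.3 excludes only "Stage V kidney disease or on renal-replacement therapy", so patients with raised baseline creatinine can enter.

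On adjudication, section 9.1 states: "Each event will be reviewed by at least 3 members". Those members must agree; otherwise the case is discussed and, if need be, voted on by at least five. Section 5.2 says the review is "based on all the data available in the chart including notes" and other records, including laboratory results. Section 9.3 places adjudication after study completion.

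**The concern.** Two limbs joined by 'or' should each do some work over the range of patients enrolled. Here the absolute limb is so small that the relative limb can never decide a case. A rise of a few percent is also of the size that repeat creatinine tests can show in a stable patient.

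At stake is the meaning of the renal event. False positives would occur in both arms, raising the reported rate, shrinking any real difference between anakinra and placebo, and spoiling the comparison with other studies that section 9.2 wants. A committee whose members read the figure differently (some literally, some silently correcting it) would no longer be applying one prespecified definition.

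**Working it through.** **1. Unit conversion.** 1 L = 10 dL, so 0.5 mg/L ÷ 10 = 0.05 mg/dL.

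**2. Where the two limbs meet.** They are equal when 0.50 × baseline = 0.05 mg/dL, that is, at a baseline of 0.05 / 0.50 = 0.1 mg/dL. Above that, the absolute limb is always reached first.

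**3. Size of the absolute limb as a relative rise** (0.05 / baseline; baselines are assumed, because the documents give none):

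| Baseline, mg/dL | 0.05 mg/dL as a rise | Same number in mg/dL (0.5) as a rise |
|---|---|---|
| 1.0 | 5.0% | 50% |
| 1.5 | 3.3% | 33% |
| 2.0 | 2.5% | 25% |

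In mg/dL the limbs would meet at a baseline of 1.0 mg/dL instead of 0.1 mg/dL. This is the internal evidence for a unit slip. It rests only on the definition itself.

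**4. Crossings by variation alone.** Inputs: one baseline and four later values (section 7.9); no true change; independent normal variation with total within-person CV of 3, 5 or 7% (assumed).

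For a single later value, the chance of a rise of at least 0.05 mg/dL is 1 − Φ(0.05 / (√2 × CV × baseline)). At 1.0 mg/dL and 5% CV this is 1 − Φ(0.05 / 0.0707) = 1 − Φ(0.707) = 0.240.

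For any of four later values against one shared baseline, with t the threshold and s = CV × baseline, the chance is 1 − ∫ φ(z) Φ(z + t/s)⁴ dz. Simulation gives the same results:

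| Baseline, mg/dL | CV 3% | CV 5% | CV 7% |
|---|---|---|---|
| 1.0 | 0.30 | 0.51 | 0.60 |
| 1.5 | 0.47 | 0.61 | 0.67 |

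**5. The same calculation with the number read in mg/dL** (rise of 0.5 mg/dL or 50%; a sensitivity check, not a proposed value). Over the same grid the largest result is 0.0014 (1.5 mg/dL, 7% CV), or about 0.1%. The contrast is not uniform: at 2.0 mg/dL, which section 6.3 allows, it is about 2% at 7% CV and about 11% at 10% CV.

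**6. Effect on a comparison of arms, if every crossing were counted.** Let p be an arm's true risk and f the chance of a false crossing, the same in both arms. The observed risk is p + (1 − p)f, so the observed risk difference is (1 − f) times the true one. With f = 0.30 to 0.67, 70% to 33% of the true difference would remain. This is an upper bound on the dilution, because adjudication may remove some crossings.

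**The case against.** The best reply is that crossings are not events. The documents do not say that every laboratory rise is referred. At least three members review the full chart and must agree, and they may be slow to call a 5% creatinine change acute renal failure. The slip may also be easy to spot: the protocol has another unit inconsistency of this kind, with BNP in ng/mL in section 6.1 and in pg/mL in sections 6.2 and 9.2. This stands as a limit on the size of the harm. It does not rescue the definition, since members who set the written figure aside are applying an unwritten one.

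A reader might infer that the adjudicated renal events would be mostly noise. The documents do not support that. Besides the referral and review steps, it needs a true event rate, which they do not give. If every crossing counted, the false share of patients meeting the definition would be (1 − q)f / ((1 − q)f + q), with q the true rate. At q = 5% and f = 0.30 this is 0.285 / 0.335 = 85%; at q = 30% and f = 0.30 it is 0.21 / 0.51 = 41%.

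A reader might also infer that a renal safety signal would be lost. That too goes beyond the documents. Section 8.1 makes renal function a safety parameter in its own right, it is scheduled at baseline and four later visits, the DSMB receives adverse event data, and the creatinine values remain available for analysis.

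Finally, the reach is small. This is one of 14 adjudicated event types, section 5.2 does not name it among the clinical outcomes, and those outcomes are labelled secondary exploratory. That is correct, and it bounds the point.

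**Conclusion.** The definition is wrong as written. The conversion and the redundancy of the 50% limb follow from section 9.2 alone and need no outside figure. A unit error is the likely explanation, but only the sponsor can confirm it.

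The size depends on assumptions. With stable creatinine of 1.0 to 1.5 mg/dL, total within-person CV of 3 to 7% and independent variation, about 30 to 67% of patients would have at least one raw crossing over four visits. The share that would become adjudicated events cannot be worked out from the documents. The direction is clear if the text is applied literally: more renal events in both arms, and a diluted difference in the time-to-event analyses and the 1-, 3- and 6-month rates. Peak VO₂ and the sample size calculation are not touched.

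**What to change.** Before adjudication starts, the sponsor should confirm the intended unit and value of the absolute limb and reconcile it with the 50% limb in section 9.2. Any adjudication form that repeats the definition should be changed to match. It would help to state at the same time which creatinine is the reference, over what window the rise is judged, and whether a repeat sample is needed, since section 9.2 is silent on all three.

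The cost is one line of protocol text and the approval that section 10.3 requires for a modification. Because section 9.3 puts adjudication after study completion, a correction made before then needs no repeat adjudication and no new data.
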